## 1.0 Study Summary

Study Title	HMH Omega-3 Covid Recovery Study
Study Design	We will conduct a two-arm, double blind randomized 12-week study to supplement omega-3 (EPA + DHA) among 100 adults (age 18+) who had covid-19 and are experiencing possible after-effects from the illness (post-acute sequelae of covid-19, also called post-covid syndrome or long covid syndrome).
Primary Objective	The primary objective is to serve as a feasibility study for omega-3 fatty acid supplementation v. placebo in adult patients to limit long covid syndrome. This will serve as a proof-of-concept for a larger follow-up study to subsequently be conducted.
Secondary Objective(s)	Determine which of the post-covid symptom(s) are most impacted by omega-3 supplement.
Research Intervention(s)/Investigational Agent(s)	Participants will be assigned to one of two study arms and asked to take an Omega-3 supplement or placebo for 12 weeks. Participants will report symptoms bi-weekly throughout the study period. A spot blood sample to assess omega-3 levels will be done at baseline and at the end of the 12-week study period.  A survey will be used bi-weekly to assess health status and outcomes via patient self-report. Data on demographics and comorbidities such as obesity and diabetes will be collected at baseline. At the end of study participation, subjects will take a follow-up survey assessing feasibility.
IND/IDE #	IND # 157250
Study Population	Hackensack Meridian Health team members age 18+ who tested positive for COVID-19 28+ days prior and who are not already taking an Omega-3 supplement.
Sample Size	50 participants in each arm = 100 total for final analysis (up to 60 participants in each arm will be recruited if needed, dependent on attrition for a total of up to 120)
Study Duration for individual participants	Individual participants will be in the study for 12 weeks. During the 12 week study period, subjects will be sent a survey every two weeks. At the end of the 12 weeks, subjects will complete a short survey collecting feasibility and acceptability data.
Study Specific Abbreviations/Definitions	
 
• Hackensack Meridian Health (HMH)
 
• Center for Healthy Senior Living (CHSL)
 

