#### **4.2 Secondary and Exploratory Outcome Variables**

A separate analysis will be conducted to determine which post-covid symptom(s) are more impacted by omega-3 supplement. The Bi-weekly Symptoms and Quality of Life Post Covid-19 Survey (Appendix C) includes the four symptoms being measured (respiratory, fatigue, lack of taste, lack of smell). Therefore, this bi-weekly survey will be used for this efficacy analysis.

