## 10.0 Inclusion and Exclusion Criteria

### Inclusion Criteria

- Team member at Hackensack Meridian Health
- Age: 18+
- Willing to provide informed consent
- Formal diagnosis of COVID-19 via PCR test (if home test was done, team member must confirm via PCR test)
- Outpatient treatment only for covid-19; no hospitalization (most team members will be vaccinated and may likely have milder case)
- Must be experiencing 1+ ongoing covid-19 symptom being measured in this study (respiratory symptoms (shortness of breath, cough), fatigue, loss of taste, loss of smell)
- Symptom(s) have persisted for more than 12 weeks after initial infection

- Symptom(s) coincided with covid-19 infection and were not present prior to covid-19 infection
- Does not have soy allergy
- Does not have allergy to fish
- Able to participate in bi-weekly surveys in REDCap
- Able to take own blood pressure and record it in bi-weekly REDCap survey
- Willing to participate in 12-week study and be assigned to either intervention or placebo arm
- Not currently taking an omega-3 supplement or other high-dose supplement (over 2,000 IU) with potential for aiding recovery of long covid syndrome (e.g. zinc, Vit C, Elderberry).
- Able to take/swallow six mini-pills daily
- Able and willing to give a spot blood sample (2 drops) at baseline and end of study.

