## **17.0 Data Management and Confidentiality**

### **17.1 Data analysis plan**

All study data will be summarized with descriptive statistics. Continuous variables will be summarized with means, standard deviations, medians and ranges. Categorical variables will be summarized with counts and percentages. Data will be summarized overall and separately by the two study arms: Omega-3 supplement or placebo. In general, continuous endpoints will be compared between groups using t-tests or Wilcoxon rank sum tests, as appropriate. Categorical endpoints will be compared between groups using chi-square tests or Fisher's exact tests, as appropriate.

The primary analysis will be the comparison of groups on the long covid-19 symptoms recovery using a chi-square test or Fisher's exact test, as appropriate.

Additional exploratory analyses may be conducted to better understand relationships within the data.

Results with a p-value less than or equal to 0.05 will be considered statistically significant. No adjustments for multiple comparisons will be implemented as this is a feasibility study not statistically powered for analyses.

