## Inclusion/Exclusion Eligibility Survey

Please complete the survey below.

Thank you!

---

1. Are you a team member at Hackensack Meridian Health?  Yes  No

---

2. Are you age 18 or over?  Yes  No

---

3. Have you tested positive for coronavirus (COVID-19) via PCR test? (Note: home test or other rapid test MUST be confirmed by a PCR test)  Yes  No

---

4. On what date were you diagnosed with Covid-19 via PCR test? \_\_\_\_\_

---

5. Have you been experiencing symptom(s) related to covid-19 for more than 12 weeks after initial infection?  Yes  No

---

6. Which of the ongoing covid-19 symptoms have you been experiencing? (please check all that apply)  Respiratory symptoms (shortness of breath and/or cough)  Fatigue  Loss of taste  Loss of smell

---

7. Were any of these symptoms present before your covid-19 infection?  Yes  No

---

8. Where you ever hospitalized for covid-19?  Yes  No

---

9. Did you require supplemental oxygen for covid-19?  Yes  No

---

10. Do you have a known soy allergy?  Yes  No

---

11. Do you have a known allergy to fish?  Yes  No

---

12. Are you able to take an online survey every other week (bi-weekly) for the study?  Yes  No

---

13. Are you able to take your own blood pressure and record it in bi-weekly online survey?  Yes  No

---

14. If you qualify, are you willing to participate in this 12-week study and be assigned to either intervention or placebo arm? This means you will be assigned to either take the omega-3 supplement or a placebo (pill with soybean oil in it).  Yes  No

Confidential

Confidential

Page 2

15. Are you currently taking an omega-3 supplement or other high-dose supplement (over 2,000 IU) with potential for aiding recovery of long covid syndrome (e.g. zinc, Vit C, Elderberry)?

 Yes No

16. Are you able to take/swallow six mini-pills daily?

 Yes No I don't know

17. Are you able and willing to give a spot blood sample (2 drops) at the beginning (baseline) and end of the study?

 Yes No

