**Please select which week you stopped experiencing the symptoms described below.**

**If you never experienced this symptom, please select N/A**

	During the first two weeks since my covid-19 diagnosis	During the third week since my covid-19 diagnosis	During the fourth week since my covid-19 diagnosis	I still experience this symptom	N/A - I never experienced this symptom
Shortness of breath					
Cough					
Fatigue					
Lack of taste					
Lack of smell					
Other					

If you answered "Other," please specify/describe additional symptom #1: \_\_\_\_\_

If you answered "Other," please specify/describe additional symptom #2: \_\_\_\_\_

If you answered "Other," please specify/describe additional symptom #3: \_\_\_\_\_

Comment - Optional (please add here anything else you might want to share with us regarding any symptoms and/or your quality of life since your covid-19 diagnosis) \_\_\_\_\_

Please write-in your blood pressure, taken anytime in the last 2 weeks: \_\_\_\_\_

Source of blood pressure (BP) equipment and method:

- BP was taken by machine at home
- BP was taken by machine at a pharmacy
- BP was taken manually in medical office

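### The symptom-by-symptom recovery analysis names no at-risk denominator, although a subject can enter with only one of the four symptoms

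*Combined protocol and SAP*

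**What the plan says.** Under section 10.0 (Inclusion Criteria) a subject "Must be experiencing 1+ ongoing covid-19 symptom being measured in this study". The list is respiratory symptoms, fatigue, loss of taste and loss of smell. The secondary objective in section 1.0 is to "Determine which of the post-covid symptom(s) are most impacted by omega-3 supplement". Section 4.2 assigns this to its own analysis: "A separate analysis will be conducted to determine which post-covid symptom(s) are more impacted by omega-3 supplement". It takes the data from the bi-weekly survey, which "includes the four symptoms being measured (respiratory, fatigue, lack of taste, lack of smell".

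The tests are in section 17.1. Data are summarised overall and by arm, and "The primary analysis will be the comparison of groups on the long covid-19 symptoms recovery using a chi-square test" or Fisher's exact test. That section does not define recovery, its time point, or whether it is per symptom or a composite, and it names no denominator. Section 12.0 gives 50 subjects per arm for analysis.

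Two instruments matter. Appendix A item 6 asks at screening "Which of the ongoing covid-19 symptoms have you been experiencing", with one box for shortness of breath and/or cough. The Appendix C grid asks when each symptom stopped. Its answers are the first two weeks, the third week or the fourth week since diagnosis, still present, or "N/A - I never experienced this symptom". It has separate rows for shortness of breath and cough.

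**The concern.** A subject who enters with fatigue alone cannot recover smell on either treatment. Counted in the smell comparison, that subject adds a fixed outcome unrelated to treatment and shrinks the difference between arms. The shrinkage is greater for rarer symptoms, so the four comparisons stop being on a common scale, which is what a ranking of symptoms needs.

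The study is meant as proof of concept for a larger efficacy trial (section 2.0). The symptom ranking is an obvious input to that trial's choice of endpoint, so a ranking that partly reflects how common each symptom was at entry could point it at the wrong one.

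**Working it through.** **1. The plan's own figure.** 2 × 50 = 100 for analysis and 2 × 60 = 120 at most recruited. No recovery rate, effect size or power is given, so 100 cannot be re-derived. Everything below uses assumed rates.

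**2. How Appendix C records a subject without the symptom at entry.**
- Never had it: the N/A answer.
- Had it, but it ended before enrolment: the only stopped answers are weeks up to the fourth since diagnosis, so one of these is ticked.

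Neither subject can benefit. Read literally, the second looks recovered, and the first is either not recovered or dropped. No section says which.

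**3. Dilution.** Let q be the share with the symptom at entry, equal in both arms, and let pC and pT be recovery among those with it.
- Others scored not recovered: q·pT − q·pC = q(pT − pC).
- Others scored recovered: (1 − q + q·pT) − (1 − q + q·pC) = q(pT − pC).

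Either way the risk difference is multiplied by q.

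**4. Power.** Assumed: pC = 0.30, pT = 0.60, two-sided 0.05 (sidedness is not stated in the plan), 50 per arm. Section 3.0 reports fatigue in 53% to 72% and dyspnea in 42% to 66% across several cohorts. These were hospitalised patients, whom section 10.0 excludes, and no rate is given for taste or smell. The range for q is therefore an assumption.

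Formula, with p̄ the mean of the two rates p1 and p2: power = Φ{[|p2 − p1| − 1.96√(2p̄(1 − p̄)/n)] / √[(p1(1 − p1) + p2(1 − p2))/n]}.

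At q = 0.45:
- Restricted, n = 22, 0.30 v 0.60: (0.300 − 0.294)/0.143 = 0.04, power 52%.
- Whole arm, others not recovered, 0.135 v 0.27: (0.135 − 0.158)/0.079 = −0.28, power 39%.
- Whole arm, others recovered, 0.685 v 0.82: (0.135 − 0.169)/0.085 = −0.40, power 34%.

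| q | At risk per arm | Whole-arm difference | Power, restricted | Whole arm, others not recovered | Whole arm, others recovered |
|---|---|---|---|---|---|
| 80% | 40 | 0.240 | 78% | 71% | 68% |
| 55% | 28 | 0.165 | 62% | 48% | 43% |
| 45% | 22 | 0.135 | 52% | 39% | 34% |
| 30% | 15 | 0.090 | 37% | 26% | 23% |

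Exact enumeration of the uncorrected chi-square test gives 52%, 40% and 35% at q = 45%, and 61%, 49% and 44% at q = 55%. Restriction gains power despite fewer subjects.

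**5. Ranking by risk difference.** A reversal needs only arithmetic. Fatigue with q = 80% and true difference 0.15 gives 0.80 × 0.15 = 0.120. Smell with q = 25% and true difference 0.35 gives 0.25 × 0.35 = 0.0875. The order flips.

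Simulations of at least 20,000 trials each used 50 per arm, control recovery 30% and independent symptoms:

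| Entry prevalence | True effects | Result counted | Whole arm | Restricted |
|---|---|---|---|---|
| 50/80/30/30% | smell +40 points, others +15 | smell ranked first | 36% | 74% |
| 50/80/30/30% | all +20 points | 80% symptom ranked first | 59% | 20% |
| 80/45/25/25% | smell +35 points, others +15 | smell ranked first | 22% | 63% |
| 80/45/25/25% | all +20 points | 80% symptom ranked first | 67% | 18% |

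With equal effects, an unbiased ranking would name each symptom about 25% of the time.

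**6. Other ranking measures.** With the others scored not recovered, the risk ratio is q·0.60/(q·0.30) = 2.0 at every q, so it is not diluted. With them scored recovered it falls, for example to 0.78/0.615 = 1.27 at q = 55%. Ranked by test statistic (80/45/25/25%, equal effects), the 80% symptom leads in 48% of trials over whole arms and still in 45% after restriction, because it has the most subjects.

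**The case against.** The strongest reply is that the plan is silent rather than wrong. Section 17.1 speaks of comparing groups and never says whole arms, and an analyst could drop the N/A answers. This stands in part: whole arms is an inference. It is the natural one, given summaries by arm, 50 per arm for analysis and no other denominator. Dropping N/A would not remove subjects whose symptom ended before enrolment.

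A reader might infer that the primary analysis itself is diluted. The documents do not support that. Recovery is undefined there, and since every subject enters with at least one measured symptom, a composite such as all entry symptoms resolved would have every subject at risk. The problem lies in the separate symptom analysis of section 4.2.

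A reader might also infer that any ranking would simply follow entry prevalence. That depends on the measure. It holds for risk differences, but not for risk ratios with the others scored not recovered. A ranking by p-value favours the common symptom even after restriction. The plan names no ranking measure.

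Finally, the primary endpoint is feasibility and section 17.1 disclaims power, so lost power alone carries limited weight, and 15 to 40 per arm will not rank four symptoms reliably under any method. That is fair. It argues for a descriptive ranking, not for leaving the denominator open until the data are seen.

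**Conclusion.** The concern holds for the symptom-by-symptom analysis behind the secondary objective. No at-risk denominator is set, and Appendix C can record subjects with nothing to recover from as recovered or as not recovered. Multiplication of the risk difference by entry prevalence is algebra and needs only equal prevalence in the two arms, which randomisation gives on average. Its size depends on assumed values. With recovery of 30% v 60% and 45% prevalence, power is 52% restricted against 35% to 40% over whole arms; at 80% prevalence the loss is modest (78% against 68% to 71%). The distortion of a ranking by risk difference is the larger effect in the scenarios shown. The documents do not establish that the primary comparison is affected, or what the entry prevalences will be.

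**What to change.** In sections 4.2 and 17.1:
- Compare each symptom's recovery only among randomised subjects who reported it in Appendix A item 6, by assigned arm. The item is answered before randomisation, so the subset does not depend on treatment.
- Treat shortness of breath and cough as one respiratory symptom, to match item 6, with recovery meaning that neither is still reported.
- Define recovery as no longer giving the still-present answer at week 12. Count a blank row as missing, not as recovery, because the survey lets subjects skip questions.
- Show the number at risk per arm, and report symptoms that appear after entry separately.
- Rank symptoms descriptively by risk difference with confidence intervals, not by p-value.

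In Appendix C, add an answer for symptoms that stopped since enrolment. The inclusion list requires symptoms lasting more than 12 weeks, while the grid's stop weeks end at the fourth week after diagnosis. A subject who recovers during the trial has no true answer at present, and restricting the denominator alone would not cure that.

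The cost is a text change, one survey option with IRB approval, and visibly smaller denominators: about 15 per arm at 30% prevalence (0.30 × 50) to 40 at 80% (0.80 × 50). The entry record is already collected.

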## **2.0 Objectives**

### **Primary Objective**

To determine the feasibility of a clinical trial for omega-3 supplementation v. placebo in medical center team members for post-covid recovery.

This will serve as a proof-of-concept for a future, grant-funded study to evaluate the efficacy of omega-3 supplementation among a larger population recovering from covid-19.

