## **16.0 Potential Benefits to Subjects**

Subjects in the omega-3 supplement arm will receive the investigational product at no cost. (Those in the placebo arm will receive placebo at no cost.). Participants will also receive two free blood spot tests measuring omega-3 levels: one at baseline, and one at the end of the 12 weeks of the study.

Overall, the potential benefits to society of this feasibility study is to determine if a larger study on omega-3 supplementation for recovery of Long Covid Syndrome is warranted.

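### Section 17.1 labels unadjusted tests significant at p≤0.05 in a study it says is unpowered, and plans no between-arm effect estimate or confidence interval

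*Combined protocol and SAP*

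**What the plan says.** Section 17.1 (Data analysis plan) summarises all data descriptively, overall and by arm: means, standard deviations, medians and ranges for continuous variables, counts and percentages for categorical ones. Arms are compared by t-test or Wilcoxon test for continuous endpoints and by chi-square or Fisher's test for categorical endpoints. It then says: "The primary analysis will be the comparison of groups on the long covid-19 symptoms recovery" "using a chi-square test or Fisher's exact test, as appropriate". The threshold follows: "Results with a p-value less than or equal to 0.05 will be considered statistically significant". The next sentence reads: "No adjustments for multiple comparisons will be implemented as this is a feasibility study not statistically powered for analyses".

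Neither section 17.1 nor any other section names a risk difference, risk ratio, odds ratio or mean difference, or a confidence interval for any quantity. This includes the feasibility and acceptability measures that section 4.1 makes the primary endpoint; under 17.1 they receive counts and percentages.

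Two sections say what the results are for. Section 2.0 (Primary Objective): "This will serve as a proof-of-concept for a future, grant-funded study". Section 16.0 describes the study's value to society as being "to determine if a larger study on omega-3 supplementation for recovery of Long Covid Syndrome is warranted". Section 12.0 sets 50 subjects per arm for analysis, with up to 60 per arm recruited if attrition requires it.

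**The concern.** The plan applies the vocabulary of a confirmatory test to comparisons that it disclaims one sentence later. The disclaimer is used only to justify making no multiplicity adjustment; it does not limit how the label may be used.

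A pilot passes three things to the next trial: the control-arm recovery rate, the range of effects still plausible, and retention and acceptability with their precision. A p-value gives none of these. With 50 per arm, *not significant* fits no effect, modest harm and a worthwhile benefit alike. In the other direction, section 4.2 names four symptoms, and a chance p≤0.05 on any one of them would carry the same label as a real finding.

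**Working it through.** **Inputs from the documents.** n = 50 per arm (section 12.0); threshold 0.05, no adjustment, chi-square or Fisher for recovery (section 17.1).

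**Assumptions.** The documents give no recovery rate, effect size or sidedness. I took two-sided tests, recovery as a yes/no outcome, chi-square without continuity correction, placebo recovery of 10% to 50%, and true gains of 10, 15 and 20 points.

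**The plan's own figure.** The 50 per arm has no effect size or power behind it, so it cannot be reproduced. Only the recruitment ceiling can be checked: (60 − 50)/60 = 16.7% loss, and 50/(1 − 0.167) = 60, which agrees.

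**Exact power at 50 per arm.** For each pair of counts (i, j), take the probability Bin(i; 50, p₁) × Bin(j; 50, p₂), and sum over the pairs where the test gives p≤0.05.

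| Placebo recovery | +10 points, chi-square / Fisher | +15 points | +20 points |
|---|---|---|---|
| 10% | 0.303 / 0.195 | 0.530 / 0.410 | 0.734 / 0.640 |
| 20% | 0.212 / 0.155 | 0.393 / 0.316 | 0.595 / 0.515 |
| 30% | 0.180 / 0.132 | 0.344 / 0.272 | 0.546 / 0.463 |
| 40% | 0.184 / 0.134 | 0.345 / 0.273 | 0.543 / 0.462 |
| 50% | 0.184 / 0.134 | 0.343 / 0.271 | 0.546 / 0.463 |

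By chi-square, a 10-point gain is missed more often than found at every rate. A 15-point gain is missed more often than found at 20% to 50% placebo recovery, but not at 10%. A 20-point gain is found more often than missed throughout.

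**What the interval would show.** The Wald 95% half-width is 1.96 × √[p₁(1 − p₁)/50 + p₂(1 − p₂)/50]. At 30% v 50%: 1.96 × √(0.0042 + 0.0050) = 0.188, about 19 points.

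**Hypothetical result.** Placebo 15/50, omega-3 20/50. The difference is 0.40 − 0.30 = 10 points. The standard error is √(0.0042 + 0.0048) = 0.0949, so the 95% CI is 10 ± 18.6, or about −9 to +29 points. Fisher p = 0.40. The planned output is two percentages and *not significant*; the interval shows that the data fit anything from modest harm to a large benefit.

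**False positives.** If four symptom tests were independent, the chance of at least one p≤0.05 with no true effect would be 1 − 0.95⁴ = 18.5%. Positive correlation between symptoms, which is likely, would lower this.

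**Feasibility proportions.** The half-width is widest at 50%: 1.96 × √(0.25/100) = 9.8 points overall and 1.96 × √(0.25/50) = 13.9 points per arm. Neither would be reported.

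**The case against.** The strongest reply is that little is lost. Section 17.1 commits to counts, percentages, means and standard deviations by arm, from which a reader can derive a difference and an interval, and it openly says that the study is unpowered. That is correct and limits the severity. What remains is that the plan does not commit to reporting the informative quantity, yet does commit to the label.

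Three stronger readings are tempting, and the documents do not support them.

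- *That not significant is the likeliest result whatever the truth.* This depends on an effect that the documents never state. Chi-square power is 55% for 20 points at 30% placebo recovery and 53% for 15 points at 10%, so significance is then the likelier outcome. The lower Fisher figures carry little weight at 30% v 50%, where expected counts are 20 and 30; Fisher would probably not be chosen there.
- *That p≤0.05 decides whether the follow-up trial goes ahead.* No section says so. Section 16.0 is a statement of societal benefit, section 4.1 makes feasibility the primary endpoint, and the threshold in 17.1 is a reporting label. The explicit numerical stopping rule, in section 15.0, concerns adverse events.
- *That 100 analysed out of 120 recruited is a retention target.* Section 12.0 makes 120 a ceiling, used only if attrition requires it. It is neither a fixed denominator nor a success criterion.

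One could also keep the p-values and simply call them exploratory. That is acceptable, and the fix allows it, provided that the estimates and intervals are added.

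**Conclusion.** The concern holds as a defect in what the plan commits to report. Section 17.1 calls unadjusted tests significant at p≤0.05 in a study that it describes as unpowered, and it plans no between-arm estimate and no interval. At 50 per arm, exact chi-square power is 18% to 30% for 10 points, 34% to 53% for 15 and 54% to 73% for 20, over assumed placebo recovery of 10% to 50%. A true gain of 10 points or less at any of these rates, or of 15 points or less at 20% to 50%, would usually appear only as *not significant*, with an uncertainty of about ±19 points (at 30% v 50%) left unstated.

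The absence of estimates and intervals is a matter of text and rests on no assumption. The power figures rest on the assumed recovery rates, two-sided testing and a yes/no recovery outcome. The trial's validity is not affected, but its stated use, informing a larger study, is poorly served. The change should be made. That 4.1 makes feasibility primary while 17.1 makes symptom recovery the primary analysis is a separate matter; this point does not depend on it.

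**What to change.** In section 17.1, replace the significance sentence with wording to this effect:

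- Between-arm comparisons will be reported as the risk difference or mean difference with a 95% confidence interval.
- Any p-values are exploratory and are not evidence for or against efficacy.
- Feasibility proportions will be reported overall and by arm, each with a 95% confidence interval.

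The cost is this wording and one added column per table. No extra subjects, data or procedures are needed, and the sample size stays as it is. The one real downside is that the sponsor gives up the option of claiming statistical significance, which a study described as unpowered is poorly placed to use.
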